### 2.5 Study design

RCT (computerized randomization; 1/1 allocation sequence; no blinding)

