Background variables	The following variables that potentially affect patient's expected live birth rate will be extracted from patient's medical file: whether they already had an ART-child (i.e. yes/no) and how many unsuccessful embryo transfers they had in the past (i.e. number). In addition, both partner's general optimism, will be assessed with the reliable questionnaire 'LOT-R' which will be disseminated in coded paper-pencil format on the day of oocyte aspiration.
Feasibility outcome	On the day of their fresh embryo transfer, men and women will be asked to fill out two questions on uptake and evaluation of the standardized personalized feedback.

Follow-up outcomes	Long-term clinical and compliance outcomes will be followed-up in couple's medical chart 12-18 months after the oocyte aspiration. More specifically, the 12-months cumulative clinical live birth rates for the observed oocyte aspiration will be extracted from the medical chart. In addition, the following compliance outcomes will be extracted: (i) censored by their medical doctor to discontinue IVF (yes-no) , (ii) number of untreated cycles within 12-months after oocyte aspiration and prior to the start of a new fresh cycle while not pregnant (i.e. IVF-delay), (iii) whether or not a subsequent IVF-cycle was started within twelve months after the last failed pregnancy test while not pregnant and no medical censoring to discontinue (i.e. IVF-discontinuation).
Study design	RCT (computerized randomization; 1/1 allocation sequence; no blinding)
Endpoints	The expected IVF live birth rate, anxiety and infertility specific distress of women and men.
Sample size	Hypothesizing that the intervention can lower the proportion of women expecting their live birth rate to be double their calculated IVF-prognosis from 50% to 25% dictates a sample size of 64 women per group (two-sided test; power 80%; $\alpha=0.05$ ; G*Power). To account for a 15% chance of study drop-out due to not filling-out the questionnaires or loss of follow-up, 74-80 women will be recruited per group .

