### 2.3 Study parameters/endpoints

The **primary endpoint** is the proportion of women expecting directly after their fresh embryo transfer that their IVF-live delivery birth rate to be double their calculated IVF-prognosis (i.e. women's expected live birth rate  $\geq 2^* \text{prognose}$ ) In addition the proportion of men expecting their IVF-live birth rate to be double their calculated IVF-prognosis will be studied. Patient's expected IVF-live birth rates will be assessed immediately after the fresh embryo transfer with a single question coded paper-pencil questionnaire.

**Women's and men's anxiety** will be assessed with the reliable 'State-Anxiety Inventory, (STAI-state)' questionnaire disseminated in coded paper-pencil format on the day of the fresh embryo transfer (Appendix 3). The STAI-state questionnaire includes 20 questions rated on a-four-point-Likert scale and results in a score between 20 to 80 (the higher, the more anxiety).

**Patient's infertility-specific distress** will be assessed with the reliable 'Infertility Distress Scale (IDS)' questionnaire, which has been translated reciprocally to Dutch (Appendix 4). The IDS questionnaire will be disseminated via text message and online within two days of the conclusive pregnancy test after the transfers of the last (fresh or cryopreserved) embryo of the studied IVF-cycle. The IDS questionnaire includes eight questions to be rated on a-five-point-Likert scale and results in a score between 8 and 40 (the higher, the more infertility specific distress, Appendix 4).

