### 2.4 Follow-up parameters/endpoints

**Long-term clinical and compliance outcomes** will be followed-up in couple's medical chart twelve-eighteen months after the oocyte aspiration. More specifically, the 12-months cumulative clinical live birth rates for the observed oocyte aspiration will be extracted from the medical chart. In addition, the following compliance outcomes will be extracted: (i) censored by their medical doctor to discontinue IVF, (ii) number of untreated cycles within 12-months after oocyte aspiration and prior to the start of a new fresh cycle while not pregnant (i.e. IVF-delay), (iii) whether or not a subsequent IVF-cycle was started within twelve months after the last failed pregnancy test while not pregnant and no medical censoring to discontinue (i.e. IVF-discontinuation;)

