### 3.2 Study procedures including recruitment and data-collection

The main outcomes of this study are gathered on the days of OPU and Embryo transfer as presented in figure 1.

[figure not shown]

Figure 1: Study procedure and data collection for participating couples of the GAP-RCT

**On the day of their oocyte aspiration**, couples will be informed on the study and asked for their informed consent. Consenting men and women of eligible couples will be asked to each fill out a questionnaire on expected live birth rate (Appendix 1) and the LOT-R questionnaire (Appendix 2) on general optimism.

**On the day of their fresh embryo transfer**, couples are randomized. Couples in the control group receive a document with a photo of their embryo(s) and the number of cryopreserved embryos. Couples in the intervention group receive a document with a photo of their transferred embryo(s), its quality rating, the number of cryopreserved embryos and couple's personalized IVF-prognosis (Appendix 5). Men and women of both groups will be asked to fill out the questionnaire on expected live birthrate (Appendix 1) and the STAI-state questionnaire on anxiety (Appendix 3).

**Within two days of the conclusive pregnancy test** after the transfers of the last (fresh or cryopreserved) embryo of the studied IVF-cycle, the IDS questionnaire on Patient's infertility-specific distress will be disseminated via text message and online (appendix 4).

**Eighteen months after the embryo transfer** of the last (fresh or cryopreserved) embryo of the studied IVF-cycle, the researchers will follow-up the long-term clinical and compliance outcomes in patient's medical chart (i.e. censored by their medical doctor to discontinue IVF, IVF-delay and IVF-discontinuation).

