The data shall be coded, which means that there continues to be a link between the data and the individual who provided it. The research team is obligated to protect the data from disclosure outside the research team according to the terms of the research protocol and the informed consent document. The subject's name or other identifiers should be stored separately from their research data and replaced with a unique code to create a new identity for the subject. Note that coded data are not anonymous.

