## 12. Appendices

### Appendix 1: Questionnaire on IVF-live birth rates expected by patients

[figure not shown]
[figure not shown]
---

Your gynaecologist told you which success rates he/she expects in your case but we are interested in your expected IVF-live birth rate.

**What, do you think, is the chance that you or your partner will deliver after all the embryo transfers of your current IVF/ICSI-cycle?**

This includes both the current fresh embryo transfer and, in case embryos have been frozen, subsequent frozen embryo transfers.

(Please indicate your response with a 'X' on the bar below, the arrows below explain the meaning of some possible answers)

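### No masking is described for extracting the follow-up outcomes from the chart, so avoidable observer bias can enter the between-arm comparison of IVF-discontinuation

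*Combined protocol and SAP*

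**What the plan says.** Section 2.5 describes the trial as "RCT (computerized randomization; 1/1 allocation sequence; no blinding", and the synopsis uses the same words. Neither says whom this covers.

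Section 3.2 assigns the long-term data to the study team: "the researchers will follow-up the long-term clinical and compliance outcomes in patient's medical chart". Two of the three compliance outcomes are linked. Outcome (i) in the synopsis is "censored by their medical doctor to discontinue IVF (yes-no". Outcome (iii), in section 2.4, is whether a further cycle was started within twelve months, assessed "while not pregnant and no medical censoring to discontinue (i.e. IVF-discontinuation". Section 4.7 compares the arms on the cumulative live birth rate and all three compliance outcomes, without naming a test.

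For the primary endpoint, section 2.3 collects the expected live birth rate "with a single question coded paper-pencil questionnaire". Appendix 1 instructs the respondent: "Please indicate your response with a 'X' on the bar below". The plan does not say who turns the mark into a percentage.

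The forms are coded, but section 7.1 presents coding as a privacy measure: "The subject's name or other identifiers should be stored separately from their research data and replaced with a unique code". Section 4 mentions no masked reading, masked extraction, second reader or coding rule for medical censoring.

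**The concern.** Couples and treating staff cannot be blinded, because the intervention is information handed to the couple. That reason does not extend to someone reading a chart a year or more later. As written, the plan leaves that person unmasked by default.

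This matters most for medical censoring. Where a couple stopped after a conversation with the doctor, the extractor may have to decide whether the doctor ended treatment or the couple did. The rationale in section 1 links unrealistic expectations to distress and then to discontinuation, so an extractor who knows the arm also knows which answer would fit the hypothesis. A lean on a few unclear notes would shift the comparison in one direction, and nothing in the data would reveal it afterwards.

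**Working it through.** **1. Which follow-up outcomes can depend on the reader**

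| Outcome (sections 2.4 and 4.7) | What the extractor does | Room for judgement |
|---|---|---|
| Cumulative live birth | Records an event | Little |
| (i) Medical censoring | Reads whether the doctor stopped treatment | Possible; no coding rule given |
| (ii) IVF-delay | Counts untreated cycles | Little |
| (iii) IVF-discontinuation | Checks for a new cycle, then applies (i) | Inherited from (i) |

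Take a couple who are not pregnant, have started no new cycle and have an unclear note. Read as medical censoring, they score yes on (i) and cannot count as discontinuing on (iii). Read the other way, they score no on (i) and count as discontinuing. One reading moves two outcomes, in opposite directions.

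**2. Size for IVF-discontinuation**

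The plan gives no discontinuation rate, number at risk or misclassification rate, so only an illustration is possible. Assume 40 couples at risk in one arm and 3 unclear charts moved out of discontinuation.

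- If reassigned couples stay in the denominator: 3/40 = 7.5 percentage points.
- If they leave the denominator, and d couples were first counted as discontinuing, the change is d/40 − (d − 3)/37 = 3(40 − d)/(40 × 37). This is 7.5 points at d = 3 and falls to 0 at d = 40.

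The plan does not say which denominator applies, so 7.5 points is the ceiling for this example. With a fixed denominator, other inputs give 1/40 = 2.5 points for one chart, 3/64 = 4.7 points if all 64 evaluable couples were at risk, and 3/80 = 3.75 points if all 80 recruited were.

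**3. Size for the primary endpoint**

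The plan's own figure comes first. For 50% against 25%, two-sided alpha 0.05, Fisher's exact test has power 0.794 at 63 per group and 0.802 at 64. This reproduces the 64 in section 3.1.2. With the planned chi-square test without continuity correction, exact power at 64 is 0.85. Masking changes none of these figures.

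For a reading error, assume prognosis follows Beta(3,7) and expectation is normal with mean 40 to 55 points and SD 20. The documents supply none of these. The endpoint is expected rate at least twice the prognosis.

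- Shifting every mark in one arm by 2 points in the same direction changes that arm's proportion by 2.2 to 2.3 percentage points. That is 64 × 0.023 = about 1.5 women, against a planned difference of 25 points.
- A consistent half-point shift changes it by about 0.5 to 0.6 points.

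Type I error with a true rate of 50% in both arms, 64 per arm and the uncorrected chi-square test, when a share of one arm's marks is read across the cut:

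| Share misread one way | Marks (64 × share) | Type I error |
|---|---|---|
| 0% | 0 | 0.045 |
| 2% | 1.3 | 0.051 |
| 3% | 1.9 | 0.058 |
| 5% | 3.2 | 0.081 |
| 10% | 6.4 | 0.202 |

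The 2-point shift falls between the 2% and 3% rows. Real distortion would need a consistent lean on 3 or more marks.

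**The case against.** A one-line design label may mean only that participants and clinicians are not blinded; it does not establish that an extractor will know the arm. That is fair, and the point should be put as masking not described. It remains a gap, because no passage supplies the masking.

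The affected outcomes are follow-up outcomes, outside the synopsis's primary and secondary lists, with no role in the sample size. Most are factual. If medical censoring is charted as an explicit entry, little is left to interpret; the documents do not say how it is charted. This limits the weight of the point but does not remove it, since section 4.7 compares the arms on these outcomes and discontinuation is central to the rationale.

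A reader might infer that researchers who know the arm read the Appendix 1 marks, and that the primary result is therefore open to material observer bias. The documents do not support this. They do not name the reader or say what that person knows. The woman places the mark herself, and locating it is measurement. Even a uniform 2-point shift in one arm is small against 25 points, and nothing suggests such a shift. The layout of the bar is in a figure not available here, so difficulty of reading cannot be judged.

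Masking the chart is also imperfect. Notes may mention the feedback, and the plan does not say whether the feedback sheet is filed there. A written coding rule for medical censoring would address the ambiguity more directly. It complements masking, because a rule still has to be applied to unclear notes.

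**Conclusion.** The point holds as a cheap improvement, not as an error. The no-blinding statement is unlimited, no masking is described for chart extraction, and the reading of medical censoring determines who can count as IVF-discontinuation. That leaves avoidable observer bias in the compliance comparison.

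Its size cannot be computed from the documents. The 7.5-point figure rests on two assumed inputs, 40 couples at risk and 3 reassigned charts, and should not be read as an estimate of likely bias. The effect on the primary endpoint is likely negligible. The sample size, alpha and power are unaffected.

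**What to change.** In section 2.5 and the synopsis, limit the no-blinding statement to participants and treating staff. In section 3.2, add that:

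- existing staff extract the follow-up outcomes, in particular medical censoring and IVF-discontinuation, from a code list that does not show allocation;
- the extractor does not open the feedback sheet, since its content differs between arms;
- any case in which a chart note reveals the arm is recorded;
- the values are locked before the arm is merged.

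The coded Appendix 1 marks can be entered in the same way at no added cost. The prognosis is needed in both arms to define the endpoint, so having it to hand does not by itself disclose the arm.

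The cost is protocol wording and a changed order of data handling. The downside is that masking will be incomplete where notes mention the feedback. It also cannot remove any influence of the arm on the doctor's advice or on the couples' own answers.

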## 3. Methodology

### 3.1 Study population and sample size

#### 3.1.1 Study population

##### Inclusion criteria:

All couples treated at the Sint Augustinus Fertility clinic (Wilrijk) with a 2nd-6th fresh cycle of IVF are eligible. IVF includes IVF with or without ICSI and every couple can only participate ones in this study. Couples treated with their first IVF-cycle are not eligible, since they are not the priority target population for this study. According to qualitative research discontinuation from IVF can amongst others be explained by the combination of high expectations regarding IVF-live birth rates and having experienced several cycles of unsuccessful IVF.

##### Exclusion criteria:

- Couples going through IVF because they have an indication for **Pre-implantation Genetic Diagnosis (PGD)** are excluded as this study explores possible associations between IVF live birth rates expected by patients and infertility specific distress. The latter is less relevant to PGD-couples who turn to IVF for a genetic indication and not because of fertility problems.
- Couples treated with **donated** oocytes, sperm or embryos
- Couples treated with spermatozoa obtained by testicular extraction (**ICSI-CRYO-TESE**)
- **HIV-positive** patients

### 3.1.2 Sample size calculation

Hypothesizing that the intervention can lower the proportion of women expecting their live birth rate to be double their calculated IVF-prognosis from 50% to 25% dictates a sample size of 64 women per group (two-sided test; power 80%;  $\alpha=0.05$ ; G\*Power). To account for a 25% chance of study drop-out due to no embryos for transfer, not filling-out the questionnaires or loss of follow-up, 80 women will be recruited per group.

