### 2.2 Study design

At the time of oocyte aspiration, patients will be randomised in two groups:

- Control group: At the time of their fresh embryo transfer couples will receive a document with a photo of their transferred embryo(s) and the number of cryopreserved embryos.
- Intervention group: At the time of their fresh embryo transfer couples will receive a document with the following feedback (Appendix 5): a photo of their transferred embryo, the number of cryopreserved embryos, the quality rating of the transferred embryo's (i.e. ★, ★★, ★★★, ★★★★, appendix 6), and couple's personalized IVF-prognosis (i.e. their chance on a live birth from the current IVF-cycle, including the transfer of fresh and if available cryopreserved embryos), calculated by entering eight background characteristics and five IVF-laboratory results into a prognostic model (Appendix 7).

Firstly, we wish to analyse whether personalized information on IVF-prognosis on the day of their fresh embryo transfer results in more realistic expected IVF-live birth rates.

Secondly, we wish to evaluate whether sharing these IVF-prognosis with patients at the time of embryo transfer is associated with the anxiety experienced by patients.

Thirdly, we wish to explore whether these IVF-live birth rates expected by patients are associated with the infertility specific distress experienced by patients at the time of a negative pregnancy test.

Fourthly, we wish to follow-up whether these IVF-live birth rates expected by patients are associated with clinical and compliance outcomes.

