### 3.3 Withdrawal of individual subjects

Subjects can stop their participation in study at any time without having to give a reason. If this happens, only the data collected until that point will be used.

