### **7.2 Recruitment and consent**

Couples will be asked for informed consent on the day of their oocyte aspiration. Patients who agree to participate will be asked to sign a written informed consent of which they will receive a copy.

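### Drop-out inflation: 80 recruited at 25% loss leaves 60 per group, not the required 64, and the synopsis gives a different rate, causes and target for the same 64

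*Combined protocol and SAP*

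**What the plan says.** Section 3.1.2 assumes that the intervention lowers the primary-outcome proportion from 50% to 25%, and says this "dictates a sample size of 64 women per group (two-sided test; power 80"%, alpha 0.05, G*Power). It then sets its allowance for each group: "25% chance of study drop-out due to no embryos for transfer, not filling-out the questionnaires or loss of follow-up, 80 women will be recruited".

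The synopsis repeats the same effect, power, alpha and 64, but continues differently: "To account for a 15% chance of study drop-out due to not filling-out the questionnaires or loss of follow-up", with the target that "74-80 women will be recruited per group". Absence of embryos for transfer is not among its causes.

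Four other sections bear on what the rate applies to:

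- Section 7.2: "Couples will be asked for informed consent on the day of their oocyte aspiration".
- Section 2.2: "At the time of oocyte aspiration, patients will be randomised in two groups".
- Section 3.2, describing the day of fresh embryo transfer: "couples are randomized. Couples in the control group receive a document with a photo".
- Section 3.3: "Subjects can stop their participation in study at any time without having to give a reason". It adds that data collected up to that point are kept.

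Section 2.3 places the primary-outcome question immediately after the transfer. Section 4.2 names a chi-square test for it and does not mention a continuity correction.

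**The concern.** The allowance for loss exists so that the required number remains after the assumed loss. In section 3.1.2 it does not. The synopsis then offers a second allowance for the same requirement, with a different rate, different causes and a different target. A reader cannot tell how many evaluable women the trial is designed to have, and whichever statement reaches the publication will conflict with the other.

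The base of the rate is also open. If recruited means consented at aspiration, having no embryo for transfer is a loss whichever day randomisation falls on. If it means randomised, that cause is a loss only when randomisation comes before transfer, and sections 2.2 and 3.2 disagree on this. Changing the percentage alone would leave the question unsettled.

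**Working it through.** **Inputs.** Proportions 0.50 and 0.25, two-sided alpha 0.05, power 80%, 64 per group (section 3.1.2 and synopsis); 1:1 allocation (section 2.5); chi-square test (section 4.2); 25% loss with 80 recruited (section 3.1.2); 15% loss with 74 to 80 recruited (synopsis).

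**Step 1: reproduce the 64.** The pooled-variance normal formula is n = [z(0.975)·√(2p̄(1−p̄)) + z(0.80)·√(p₁(1−p₁)+p₂(1−p₂))]² / (p₁−p₂)², with p̄ = 0.375:

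[1.960 × √0.46875 + 0.842 × √0.4375]² / 0.0625 = 57.7, so 58.

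That is not 64. Full enumeration of the two binomials with a two-sided Fisher test gives 79.4% power at 63 and 80.2% at 64, so 64 is the smallest Fisher size. That G*Power was run with Fisher's test is an inference; the plan does not name the test.

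**Step 2: the inflation.** Evaluable = recruited × (1 − d); recruitment needed = n / (1 − d), rounded up.

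| Source | Loss d | Recruited | Evaluable | Needed for 64 | 64 × (1 + d) |
|---|---|---|---|---|---|
| Section 3.1.2 | 25% | 80 | 80 × 0.75 = 60 | 64/0.75 = 85.3 → 86 | 80 |
| Synopsis, low | 15% | 74 | 74 × 0.85 = 62.9 | 64/0.85 = 75.3 → 76 | 73.6 → 74 |
| Synopsis, high | 15% | 80 | 80 × 0.85 = 68 | 76 | – |

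Both 80 (section 3.1.2) and 74 (synopsis) match 64 × (1 + d), which points to one repeated slip. To keep 64 evaluable, 80 recruited tolerates 1 − 64/80 = 20.0% loss, and 74 tolerates 1 − 64/74 = 13.5%.

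**Step 3: exact power at the resulting sizes.** Full enumeration, 50% versus 25%, two-sided 0.05:

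| Per group | Uncorrected chi-square | Continuity-corrected | Fisher |
|---|---|---|---|
| 60 | 81.8% | 76.0% | 76.0% |
| 62 | 83.4% | 78.3% | 78.3% |
| 63 | 84.3% | 79.3% | 79.4% |
| 64 | 84.9% | 79.9% | 80.2% |
| 68 | 86.3% | 81.6% | 82.3% |

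The 62.9 of the synopsis lies between the rows for 62 and 63. As a check, the pooled normal formula gives 81.6% at 60.

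**Step 4: smallest size with 80% exact power, and recruitment needed.**

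| Test | n per group | At 25% loss | At 15% loss |
|---|---|---|---|
| Uncorrected chi-square | 59 | 59/0.75 = 78.7 → 79 | 59/0.85 = 69.4 → 70 |
| Fisher | 64 | 86 | 76 |
| Continuity-corrected | 65 | 65/0.75 = 86.7 → 87 | 65/0.85 = 76.5 → 77 |

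So 80 recruited at 25% loss is enough only for the uncorrected chi-square test; 80 at 15% is enough for all three.

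**The case against.** The strongest reply is that nothing is lost in practice. Section 4.2 names a chi-square test and the documents mention neither a correction nor Fisher's test. Read plainly, that is the uncorrected test, for which 59 per group suffices and every recruitment and loss pairing in the documents exceeds 80% power. This stands as a limit on the consequence. It does not rescue the text: on that reading the stated 64 is unexplained, and 80 at 25% loss still does not deliver it.

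A second reply is that 60 is a floor. The primary outcome is collected immediately after transfer, and section 3.3 keeps data gathered before withdrawal, so later loss does not remove it. If recruited means randomised, and randomisation is on the transfer day, having no embryo for transfer is not a loss either. This also stands. The 25% is not split by cause, so 60 holds only if all of the loss falls between recruitment and the post-transfer questionnaire.

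Third, the synopsis shortfall is small: 62.9 is about one woman under 64, and the upper target of 80 is ample at 15%. Agreed. The clear arithmetic error is the 80 in section 3.1.2. The conflict between the two statements remains.

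**Conclusion.** The point holds. On its own figures, section 3.1.2 yields 60 evaluable women per group against a stated need of 64, a shortfall of 4 (6 in recruitment, 80 against 86). The synopsis contradicts it on rate, causes and target, and implies about 63 to 68.

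The size of the consequence depends on the test. Power at 60 is 81.8% for the uncorrected chi-square and 76.0% for a corrected or Fisher test. No loss of power is shown under the plain reading of section 4.2. What is shown is that the stated sample size is not delivered by the stated drop-out rate, and that two current passages disagree. The power figures rest on the plan's 50% and 25%, equal groups, and all assumed loss removing the primary outcome. The correction should be made; it does not call the design into question.

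**What to change.** 1. Give one drop-out rate, one list of causes and one recruitment target in the synopsis and section 3.1.2, and compute evaluable women as recruited × (1 − d).
2. Say whether recruited counts women consented or women randomised, and reconcile sections 2.2 and 3.2 on the day of randomisation. Define loss of follow-up; only loss before the post-transfer questionnaire affects the primary outcome.
3. Name the test behind the 64, state in section 4.2 whether the chi-square is uncorrected, and restate the requirement and power to match:
   - Uncorrected, 80 at 25%: requirement 59, 60 evaluable, about 82% power.
   - Fisher or corrected, 80 at 25%: 60 evaluable, about 76% power; or recruit 86 (Fisher) or 87 (corrected) to hold 80%.
   - 80 at 15%: 68 evaluable, about 86% power (uncorrected) or about 82% (Fisher or corrected).

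The cost is text in the synopsis and sections 2.2, 3.1.2, 3.2 and 4.2. No extra enrolment is needed if the sponsor keeps 80 and reports the power that follows, though that figure may be less favourable. Holding 80% power with a Fisher or corrected test at 25% loss would cost 6 or 7 more women per group.
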